Dependency	3	20, 23, 24	20, 23, 24
Driving	3	15c, 16, 16a	15C, 16, 16A
Colour vision	1	12	12
Peripheral vision	1	10	10

Averaging the means for each scale for each patient, excluding the General health score, provides a composite score for each patient, which can then be used to calculate the composite score for each treatment group.

The mean for each sub-scale per patient is calculated as;

$$Mean = \frac{(Sum \ of \ score \ for \ each \ item \ with \ non-missing \ answer)}{(Total \ number \ of \ items \ with \ non-missing \ answers)}$$

The Visual Functioning Questionnaire consists of 25 questions, two with one or three sub-questions designed to elucidate the answer to the main question. The main questions are annotated as ORRES_VFQ201 to ORRES_VFQ225. The sub-questions are annotated as ORRES_VFQ215A to ORRES_VFQ215C and ORRES_VFQ216A. The values are integer numbers from 1 to 2, 3, 4, 5 or 6 depending on the number of response categories,

7.10 Safety Evaluation

All evaluations of safety data will be performed using the safety analysis set. Some information may only be found in text fields of the eCRF. Evaluations incorporating information not available from the eCRF will thus not be possible.

7.10.1 Extent of Exposure

The protocol specifies the following dosing regimen. On Day 0, the first study drug application will be at the clinical research centre. Thereafter, study drug will be self-administered at home. When the subject is at the clinical research centre for assessments, subjects will apply the study drug themselves at the clinical research centre. On Days 0 to 5, subjects will apply study drug every hour daytime only (1 drop of each ophthalmic solution in the affected eye). On Days 6 to 12, (1 week), subjects will apply study drug every 2 hours daytime only. On Days 13 to 19, (1 week), subjects will apply study drug every 3 hours daytime only. On Day 20 until resolution, subjects will apply study drug 4 times a day at daytime only. Subjects will be treated for the maximum of 1 year after randomization.

Summary statistics on the duration of exposure will be presented.

LINK Medical Study ID: PSR012

7.10.2 Adverse Events

AEs data will be captured and encoded by system organ class (SOC) and the lowest level term (Medical Dictionary for Regulatory Activities, current version). A listing of AEs will be created. This listing, at minimum, will contain a description of AEs as to seriousness, severity, onset date and end date, duration, action taken (if any), outcome and likelihood of drug causation ("relation"). A frequency table will be compiled for AEs by treatment group, SOC, and lowest level term. Frequency tables will be compiled showing the number of subjects per treatment group affected by one or more (related) AEs, including percentages, the total number of AEs per treatment group and the average number of AEs per subject exposed to the respective treatment for the following:

- AEs.
- Serious AEs.
- AEs leading to withdrawal of the IMP.
- Fatal AEs.
- AEs, broken down by severity.
- AEs, broken down by causality assessment.

There will also be tables on the most frequently reported AEs, on system organ class level and on preferred term level. The decision on the frequency cut-off for these tables will be taken during the analysis of the AEs data in consultation with the author of the clinical study report and could be influenced by factors such as the overall number of AEs, study design, and the nature of the indication. The frequency cut-off should be mentioned in a table note.

The second secondary hypothesis, as specified in the protocol, is that AEs, and those relating to toxicity in particular, are less with PHMB 0.08% monotherapy compared to the comparator. This translates into:

Hypothesis: Rate of AEs is equal in the PHMB 0.08% monotherapy is equal to that of the comparator. In particular:

Hypothesis: Rate of toxicity-related AEs is equal in the PHMB 0.08% monotherapy is equal to that of the comparator

The null hypothesis is that rate of occurrence of AEs and toxicity-related AEs are equal for the two treatment arms.

If these are rejected, the conclusion is that the rates are different, and less with PHMB 0.08% monotherapy than for the comparator if the latter rate is higher. The AETOXGR will be used to assess toxicity rates.

These will be tested using ordinal logistic regression model and model-based estimates of the difference between treatments. Odds ratio with corresponding CIs and p-values will be provided. Covariate variables such as treatment, age and sex will be included.

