5.1 Sample Size

A total of 130 subjects affected by *Acanthamoeba* keratitis will be assigned to one of the above two treatment groups in a ratio of 1:1.

The protocol states, in section 7.6:

"From the results of the sponsor's observational, case series retrospective study 038/SI, a CRR_12 of 67% for the conventional combination therapy of PHMB 0.02% and propamidine 0.1% is expected. This figure is in the range of cure rates described in the literature. If the true difference in CRR_12 is 0.20 (Δ) (or more) in favour of PHMB monotherapy (0.08% PHMB), a total sample size of 116 subjects (allowing for 10% loss to follow-up) should give the study at least 80% power to detect superiority, with 2-sided alpha=0.10 (or equivalently 1-sided alpha=0.05).

LINK Medical Study ID: PSR012

Assuming a prevalence of late stage disease, and worse outcomes, in 38% of subjects, the expected CRR_12 in the control group will be reduced from 67% to 63%. To account for the inclusion of this group, the sample size has been adjusted to 130 subjects (allowing for 10% loss to follow-up, i.e. 116 evaluable subjects).

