7.6 Medical History and Concurrent Diseases

Medical history and concurrent diseases will be coded according to the latest available version of Medical Dictionary for Regulatory Activities (MedDRA).

For each system organ class and preferred term, the number and percentage of subjects with at least one condition in that system organ class or preferred term will be presented. Medical history and concurrent diseases will be presented in separate tables, based on the safety analysis set.

Medical history is defined as events stopped prior to study inclusion. Concurrent diseases are defined as ongoing events and events stopped on or after baseline. If the start and/or stop date is partially unknown, the following imputation rules will be used for the purpose of classifying the events:

Table: Imputation of missing parts of dates

	Imputed start date	Imputed end date
Unknown year	Missing	Missing
Unknown month	1 January	31 December
Unknown day	First of month	Last of month

If it is not possible to classify the condition based on the reported and/or imputed start and end dates, it will be considered as concurrent. In data listings, the dates will be presented as reported.

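### The only full by-term adverse event table is at lowest level term; preferred-term tables stop at an unstated cut-off chosen during the analysis

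*SAP*

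**What the plan says.** SAP 7.10.2 sets the coding level first: "AEs data will be captured and encoded by system organ class (SOC) and the lowest level term". It then plans one by-term table with no cut-off: "A frequency table will be compiled for AEs by treatment group, SOC, and lowest level term". Protocol 7.5.1 and the safety paragraph of the protocol synopsis carry the same sentence, and neither plans a preferred-term table.

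A second group of tables is described by its counts: "Frequency tables will be compiled showing the number of subjects per treatment group affected by one or more (related) AEs, including percentages". SAP 7.10.2 lists these for all AEs, serious AEs, AEs leading to withdrawal, fatal AEs, and AEs by severity and by causality. It names no dictionary level for them.

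The preferred term enters for AEs only here: "There will also be tables on the most frequently reported AEs, on system organ class level and on preferred term level". On the threshold the SAP says "The decision on the frequency cut-off for these tables will be taken during the analysis of the AEs data", and that it "could be influenced by factors such as the overall number of AEs, study design, and the nature of the indication". No value is given, nor whether it applies to all subjects or within an arm. It must be disclosed in a table note.

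For medical history, SAP 7.6 uses the other level, in full: "For each system organ class and preferred term, the number and percentage of subjects with at least one condition".

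**The concern.** The lowest level term is the most detailed level of MedDRA, and several such terms can sit under one preferred term. The preferred term is the level at which different wordings of one event come together. A table by lowest level term can therefore show one clinical event as several small rows.

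The preferred-term tables would repair this, but only for events above the cut-off. Under SAP 5.2 the code is broken after database lock, and nothing in 7.10.2 requires the cut-off to be set before then. It could be chosen with the arms known.

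What is at stake is whether the report shows how often each specific event occurred in each arm. Additional safety information on 0.08% PHMB is a stated aim (protocol 2.2, SAP 3.3). The events reported most often in Phase 1 were particular ocular ones, namely conjunctival and corneal staining, pain after instillation and conjunctival hyperaemia (protocol 1.1.2). A SOC total will not separate events of that kind when they fall in the same SOC.

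**Working it through.** The documents give no figure on this point, so there is none to reproduce. The check compares the text and then sizes the gap by illustration.

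**1. Level of each planned display**

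| Display | Level | Cut-off |
|---|---|---|
| AE table by arm, SOC and term (SAP 7.10.2, protocol 7.5.1) | lowest level term | none |
| All, serious, withdrawal, fatal, severity and causality tables (SAP 7.10.2) | not named | none |
| Most frequent AEs (SAP 7.10.2) | SOC and preferred term | unstated, set during analysis |
| Medical history (SAP 7.6) | SOC and preferred term | none |

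No row gives all AEs by preferred term.

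**2. Inputs for the illustration**

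- SAP 5.1 plans 130 subjects, who "will be assigned to one of the above two treatment groups in a ratio of 1:1", so 130 / 2 = 65 per arm.
- The cut-off *c* is not in the documents. I assume 2%, 5% and 10%.

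**3. Largest count left out of the preferred-term table**

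The largest number of subjects strictly below a cut-off *c* on *n* subjects is ceil(*c* × *n*) − 1.

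| *c* | On all subjects, n = 130 | In either arm, n = 65 per arm |
|---|---|---|
| 2% | ceil(2.6) − 1 = 2 in total | ceil(1.3) − 1 = 1 per arm |
| 5% | ceil(6.5) − 1 = 6 in total | ceil(3.25) − 1 = 3 per arm |
| 10% | ceil(13) − 1 = 12 in total | ceil(6.5) − 1 = 6 per arm |

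**4. Most uneven split that would be left out, with the cut-off on all subjects**

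Fisher's exact two-sided p is used only as a yardstick of imbalance. The SAP plans no test by term.

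- *c* = 5%: 6 v 0 is 6/65 = 9.2% v 0%. p = 2 × C(65,6)/C(130,6) = 0.028.
- *c* = 10%: 12 v 0 is 12/65 = 18.5% v 0%, p = 0.0003.

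**5. What the full table would show instead**

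If the 6 subjects in the 6 v 0 case were coded evenly to three lowest level terms (an assumption), the table would have three rows of 2 v 0. Each row has p = 2 × (65 × 64)/(130 × 129) = 0.50. The arm pattern for the event as a whole would appear in no by-term display.

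**The case against.** The best case against is that this is a matter of presentation with little consequence, and much of that stands.

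- A reader might infer that all the AE tables are at lowest level term. Only one is stated to be; the others name no level.
- A reader might infer that moderately frequent events are hidden. Take 10 v 2 with 65 per arm (p = 0.030). That is 12/130 = 9.2% overall and 10/65 = 15.4% in one arm. It appears in the preferred-term table at any overall cut-off up to 9.2%, or any either-arm cut-off up to 15.4%. The loss is confined to events below the cut-off.
- A reader might infer that the secondary hypothesis of fewer AEs is compromised. SAP 7.10.2 tests it by ordinal logistic regression on AEs and toxicity-graded AEs, and the dictionary level does not enter.
- Many important ocular outcomes have their own displays: slit-lamp signs (SAP 7.9.3), intraocular pressure, ophthalmoscopy, worsening, relapse and surgery (7.10.5 to 7.10.9), and secondary complications (7.10.12).
- Protocol 8.2 asks for concise medical terms and, where possible, a diagnosis, which limits splitting. The AE listing keeps every event.
- The factors named for the cut-off do not include a difference between arms.
- The mock tables are in the Data Display Plan (SAP 7.1.1), which I have not seen and which may show preferred terms.

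Two things remain. Events below the cut-off still have no display by arm at preferred-term level, and the separate ocular displays do not cover every tolerability event. If the Data Display Plan does use preferred terms, the SAP text disagrees with it and still needs correcting.

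**Conclusion.** The point holds as a gap in descriptive safety reporting. An AE below the cut-off would be seen by arm only as lowest level rows, possibly split, and within its SOC total.

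The size depends on a cut-off that the documents do not give. At an assumed 5% of all subjects, a preferred term with up to 6 subjects is omitted. At 5% in either arm, the limit is 3 per arm. These figures use the planned 65 per arm. How far an event would split across terms is unknown; that it can do so follows from how MedDRA is built, which the documents do not spell out, although SAP 7.10.2 does treat the two levels as distinct.

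The any-AE, serious, withdrawal and severity totals, the model-based test of the AE hypothesis and the separately tabulated ocular outcomes are unaffected, and no data are lost. The documents permit the cut-off to be chosen after unmasking, but they do not support a claim that it would be chosen to suit the result.

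**What to change.** In SAP 7.10.2 and protocol 7.5.1 (and the matching synopsis sentence):

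- Make the full AE table by treatment group, SOC and preferred term, without a cut-off, counting each subject once per term.
- Use the same level wherever the serious, related and withdrawal tables are shown by term.
- Keep the lowest level term in the listings.
- State the cut-off for the short table, and whether it applies to all subjects or in either arm, before unmasking. The clean file report, which SAP 5.2 already requires to be signed before the code is broken, is a natural place to record it.
- Check that the Data Display Plan agrees.

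The preferred term comes with the same coding, so the cost is wording and routine programming. Verbatim detail stays available in the listings.

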2.3. Hypothesis

The primary hypothesis to be tested is that the CRR_12 of subjects treated with 0.08% PHMB monotherapy, is superior, or worse by no more than an acceptable pre-defined 0.20 non-inferiority margin (Δ), compared to the CRR_12 of a 0.20 PHMB + 0.1% propamidine combination therapy, administered according to the Treatment and Follow-up Protocol described in Section 5.3, which is based on a consensus of currently clinical guidelines.

Secondary hypotheses are:

- That adverse events, and those relating to toxicity in particular, are less with PHMB 0.08% monotherapy compared to the comparator.
- That time to a cure is shorter in subjects receiving PHMB 0.08% monotherapy compared to the comparator.

Note: The estimated CRR_12 from the start of treatment is 67% for the conventional (0.02% PHMB + 0.1% propamidine) combination therapy (from the sponsor's observational, case series retrospective study 038/SI²⁰) (63% when assuming a prevalence of late stage diseases in 38% of subjects).

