8.2.1. Severity Assessment

The intensity of AEs will be graded using the following scale:

- **Mild (Grade I)**: Asymptomatic or mild symptoms not interfering with the normal activity of the subject: clinical or diagnostic observations only; intervention not indicated.
- **Moderate (Grade II)**: Minimal, local or non-invasive intervention indicated; limited ageappropriate instrumental activities of daily living.

- **Severe (Grade III)**: Severe or medically significant but not immediately life-threatening: hospitalization or prolongation of hospitalization indicated; disabling; limiting self-care activities of daily living; incapacitating with inability to work or perform normal daily activity.
- Life-threatening (Grade IV): consequences: urgent intervention indicated.
- **Death (Grade V)** related to AE.

If an AE has multiple aspects, the aspect with the highest severity will be graded.

Note the distinction between the gravity (seriousness) and the intensity (severity) of an AE. Severe is a measure of intensity; thus, a severe reaction is not necessarily a serious reaction. For example, a headache may be severe in intensity, but would not be classified as serious unless it met one of the criteria for serious events listed above.

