7.2.3 Safety Analysis Set

All subjects who have received at least one dose of study medication will be included in the Safety Analysis Set. This set will be used in all analyses of safety data.

Analysis on the safety analysis set will be based on the actual treatment (i.e. subjects will be analysed 'as treated').

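### SAP 7.10.2 states a null about how often AEs occur, but its ordinal model, on the natural reading of AETOXGR, compares how severe the recorded AEs are

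*SAP*

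**What the plan says.** Protocol 2.3 lists as a secondary hypothesis: "That adverse events, and those relating to toxicity in particular, are less with PHMB 0.08% monotherapy compared to the comparator". SAP 7.10.2 turns this into a null: "The null hypothesis is that rate of occurrence of AEs and toxicity-related AEs are equal for the two treatment arms". On the method it says: "These will be tested using ordinal logistic regression model and model-based estimates of the difference between treatments". The variable is introduced with "The AETOXGR will be used to assess toxicity rates", and the model terms with "Covariate variables such as treatment, age and sex will be included".

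The SAP does not state the dependent variable for the all-AE hypothesis, whether a row is an event or a subject, or how a subject without an AE is scored. Protocol 8.2.1 introduces its five grades with "The intensity of AEs will be graded using the following scale"; the lowest is Grade I (mild), and there is no level for having had no AE. SAP 7.2.3 defines the population: "All subjects who have received at least one dose of study medication will be included in the Safety Analysis Set". Subjects without an AE therefore belong to the comparison.

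Occurrence itself (subjects affected, "the total number of AEs per treatment group and the average number of AEs per subject exposed to the respective treatment") appears in SAP 7.10.2 only as frequency tables. SAP 7.1.7 sets 0.05 for secondary hypotheses other than time to resolution.

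**The concern.** The hypothesis asks whether fewer AEs occur. An ordinal logistic model compares the distribution of an ordered outcome. If that outcome is a grade carried only by AE records, subjects with no AE contribute nothing, and the model asks whether AEs, once they occur, are milder.

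Two errors could follow. A real reduction in the number of AEs could go undetected because the grade mix is unchanged. Conversely, a rejection driven by severity mix, or by several records from one subject being treated as independent, could be reported as a difference in AE rates. SAP 7.10.2 reads a rejection as a difference in rates, and as fewer AEs on 0.08% PHMB when the comparator's rate is the higher one. This is one of two formally stated secondary hypotheses, so the conclusion carries weight.

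**Working it through.** **The plan's own figure.** The documents give no power, AE frequency or effect size for this hypothesis. The only related figure is the total of 130, set for CRR_12. It reproduces with unpooled variance at 63% v 83%, two-sided alpha 0.10 and 80% power: n = (0.63×0.37 + 0.83×0.17) × (1.645 + 0.842)² / 0.20² = 57.8, so 58 per arm. Then 116 / 0.9 = 128.9, i.e. 130 for equal arms. It supplies the 65 per arm used below and says nothing about power for AEs.

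**Why grade per record is blind to occurrence.** If an arm has n subjects with mean λ AEs and grade probabilities π_j, the expected number of grade-j records is n·λ·π_j. The share of grade j among records is n·λ·π_j / (n·λ) = π_j, so λ cancels. With an assumed grade split of 60/30/10:
- control, mean 2: 65 × 2 = 130 AEs, split 78 / 39 / 13;
- 40% fewer, mean 1.2: 65 × 1.2 = 78 AEs, split 46.8 / 23.4 / 7.8.

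Both arms are 60/30/10, and the odds ratio is 1 although 52 AEs have been avoided. Worst grade among affected subjects picks up some signal, because a subject with more AEs has more chances of a high grade, but it still omits everyone with none.

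**Simulation inputs.** From the documents: 65 per arm and two-sided 0.05. Assumed: equal follow-up; control means of 0.94 to 3 AEs per subject; Poisson or overdispersed (gamma shape 1.5) counts; the same 60/30/10 split in both arms. The low mean comes from the 61.1% AE rate in the Phase 1 study of healthy subjects (Protocol 1.1.2): 1 − exp(−μ) = 0.611 gives μ = 0.94. Grade outcomes use the proportional-odds score test (tie-corrected Wilcoxon); counts use the log rate ratio with empirical variance. Age and sex are left out.

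**AEs truly 40% fewer, same grades:**

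| Outcome | Rejection |
|---|---|
| Grade, one row per AE | 4-15% |
| Worst grade, affected subjects only | 5-28% |
| Worst grade, all subjects, no AE = 0 | 34-66% |
| Any AE, yes/no | 29-64% |
| AE count per subject | 52-100% |

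**No difference between arms.** Grade per AE record rejects about 5% with independent grades, and about 8-16% at a within-subject correlation of 0.3. All these ranges are approximate to a few points.

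**AEs halved.** A second set of runs assumed means of 1, 2 or 4, a 60/30/9/1 split and correlation 0.2. Grade per record rejects 6-13%, no higher than its own 7-18% when nothing differs. Worst grade among affected subjects rejects mostly 8-22%, reaching 50% at 4 AEs per subject with Poisson counts. Worst grade with a zero level rejects 51-87%, any AE 41-88%, and counts 72-100%.

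**Same occurrence, milder grades** (latent shift 0.4, means 1 and 2). Grade per record rejects 44-70% and worst grade among affected subjects 28-39%. Worst grade with a zero level rejects 8-15%, and any AE about 5%. The first two outcomes respond mainly to severity.

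**The case against.** The strongest reply is that the SAP never says grade is the outcome of the all-AE model. AETOXGR is tied to toxicity rates only. All treated subjects are in the safety set, which is compatible with worst grade per subject and a no-AE level. Scored that way, the model performs about like an any-AE test (34-66% v 29-64%). The documents also often use rate for a proportion of subjects: the Phase 1 dose-limiting-event rate is 5 of 90, and relapse is a rate of subjects. On that meaning, almost nothing is lost.

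This stands as a limit on the point. A reader might infer that the plan loses a large amount of power however it is read. It does not: against a count test, worst grade with a zero level loses only about 16 to 20 points at a mean of 0.94, and against an any-AE test essentially nothing. A reader might also infer that any rejection would be reported as fewer AEs with 0.08% PHMB. The SAP makes that direction conditional on a higher comparator rate, and the occurrence tables would show it.

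The reply does not remove the problem. The reading that rescues the model needs a level found in neither the Protocol's grade scale nor the SAP. Even then, the result is an odds ratio for grade, not a comparison of rates.

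**Conclusion.** The point holds in conditional form. The stated null concerns occurrence; the named model, with AETOXGR modelled where it exists, concerns severity given an event. On that reading, a true 40% reduction in AEs is declared in about 4-28% of trials, against 52-100% with a count test. The record-level form has a type I error of about 8-16% at a within-subject correlation of 0.3. If a zero level was intended, power is close to that of an any-AE test and below that of a count test, and the defect is that outcome, unit and scoring are unspecified.

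The percentages rest on assumed AE frequencies, overdispersion, grade mix and correlation, since the documents give none for this population. The mismatch between null and model does not depend on them. It affects a secondary hypothesis only and leaves the CRR_12 analysis untouched.

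**What to change.** Before the code is broken, amend SAP 7.10.2 as follows.

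- State what rate means. If it is AEs per subject, fit a negative binomial model to the number of AEs in every Safety Analysis Set subject, counting zero for those with none. Use treatment, age and sex as terms and log follow-up or exposure time as offset, and report the rate ratio with its CI. The offset is needed because treatment stops at resolution, so time at risk differs between subjects; say which time is used.
- If it is subjects affected, fit a logistic model for any AE with the same covariates.
- Do this for all AEs and for toxicity-related AEs. Identify the latter by a written rule using data already collected, such as the causality rating in Protocol 8.2.2. A grade alone does not identify them.
- Keep AETOXGR as worst grade per subject, with no AE scored 0, as a descriptive severity comparison.

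The cost is SAP wording and one changed model statement. No new data are needed.

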8.1.5. Serious Adverse Events

An AE that meets 1 or more of the following criteria/outcomes is classified as serious:

- Results in death.
- Is life-threatening (i.e., at immediate risk of death).
- Requires in-patient hospitalization or prolongation of existing hospitalization.
- Results in persistent or significant disability/incapacity.
- Is a congenital anomaly/birth defect (i.e., in an offspring to the study subject).

Other medically important AEs that may not result in death, be life threatening, or require hospitalization may be considered serious when, based upon appropriate medical judgment, they may jeopardize the subject or may require medical or surgical intervention to prevent one of the outcomes listed above. Examples of such events are intensive treatment in an emergency room or at home for allergic bronchospasm, that does not result in hospitalization. Any suspected transmission of an infectious agent via the study drug shall also be considered serious.

Serious also includes any other event that the investigator or Sponsor judges to be serious. Some events (such as, for example, corneal vascularization, corneal ulceration, corneal perforation, corneal scarring, non-infectious scleritis) are known to be a consequence of *Acanthamoeba* keratitis and therefore are expected to occur during the study. The investigator is recommended to consult the Investigator's Brochure¹⁰.

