8.2.2. Causality Assessment

For each AE, the investigator must make a causality assessment to determine if there is a reasonable possibility that the study drug caused the AE.

The relationship of any AE to the study drug will be assessed and graded on a five point scale.

Unrelated: Sufficient information exists to indicate that causality is unrelated to drug i.e. the event is due to extraneous causes (an underlying medical condition, concurrent drugs, environmental factors etc.)

The AE is likely to have been produced by the subject's clinical state, environmental or toxic factors or other therapeutic interventions but an effect of drug cannot be ruled

out.

Unlikely:

Possible: The AE follows a reasonable temporal sequence from drug administration; is unlikely to have been produced by the subject's clinical state, environmental or toxic factors

or other therapeutic interventions.

Probable: The AE follows a reasonable temporal sequence from drug administration, or is associated with established drug concentration in body tissues; improves on stopping or reducing drug dosage (de-challenge); and could not reasonably be explained by the study subject's clinical state environmental or toxic factors, or other therapeutic interventions. (Note: - There are exceptions when an AE does not disappear upon discontinuation of the drug. For example: bone marrow depression, fixed drug

eruptions, tardive dyskinesias, etc.).

Related: As for "probable" - but on the basis of the observation of objective clinical signs any

other cause may be excluded.

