6.3 Secondary safety endpoints assessment

6.3.1 AEs

Recording of AEs will commence with signing of the ICF. AEs will be captured in the CRF. AEs will be followed up by the investigator as specified in section 8 of the protocol, AE Reporting. Standard CDISC STDM annotation is being used for AE data.

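### SAP 7.10.2 tests the toxicity hypothesis on AETOXGR, which neither document defines; if it is the AE intensity grade, as seems most likely, keratitis complications enter the test alongside drug effects

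*SAP*

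**What the plan says.** Protocol 2.3 states as a secondary hypothesis: "That adverse events, and those relating to toxicity in particular, are less with PHMB 0.08% monotherapy compared to the comparator". SAP 7.10.2 turns the toxicity part into a null hypothesis: "Rate of toxicity-related AEs is equal in the PHMB 0.08% monotherapy is equal to that of the comparator". It names one variable for it, "The AETOXGR will be used to assess toxicity rates", and one method: "These will be tested using ordinal logistic regression model and model-based estimates of the difference between treatments". Treatment, age and sex are the covariates. If the null is rejected and the comparator has the higher rate, the conclusion is that toxicity is lower with 0.08% PHMB.

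The protocol has two separate AE scales. Section 8.2.1 grades severity from I to V: "The intensity of AEs will be graded using the following scale". Section 8.2.2 grades cause, from unrelated to related: "The relationship of any AE to the study drug will be assessed and graded on a five point scale". The AE recording list in protocol 8.6 includes severity and relation to study medication, but no toxicity item. SAP 7.10.2 uses causality only in frequency tables.

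Protocol 8.1.5 lists corneal ulceration, perforation, scarring, vascularization and non-infectious scleritis as consequences of the keratitis that "therefore are expected to occur during the study". SAP 7.10.12 takes secondary complications of this kind from the AE data.

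**The concern.** The hypothesis is about harm caused by the drops. An intensity grade records how bad an event was, not what caused it. If all AEs enter the model by grade, a complication of uncontrolled keratitis counts in the same way as a drug reaction.

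The arms are planned to differ in cure rate, so they would also be expected to differ in disease complications. That difference would carry over into the toxicity test. At stake is a named secondary hypothesis with its own p-value and decision rule, for a product at four times the comparator's PHMB concentration. The primary analysis is not affected.

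**Working it through.** **What AETOXGR is.** Neither document defines it. Four things point to the intensity grade:

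- its name;
- the SAP 6.3.1 statement "Standard CDISC STDM annotation is being used for AE data";
- the ordinal model, which needs an ordered response;
- protocol 8.2.1, the only AE scale with numbered grades.

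This is an inference. If the eCRF fills AETOXGR only for toxic events, the rule for calling an event toxic is missing instead.

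**Whether keratitis complications reach the test.** They are in the AE data (SAP 7.10.12). Clinically significant worsening of existing signs is an AE (protocol 8.1.3). No rule in SAP 7.10.2 removes unrelated events.

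**Size.** The plan gives no figure for this test, so there is none to reproduce. From the documents: 130 subjects randomized 1:1, so 65 per arm if all are dosed; control cure 63%; planned difference 0.20, so 83% on test. The uncured proportion u is 0.17 on test and 0.37 on control. Tests are two-sided at 5% (SAP 7.1.1, 7.1.7), so 2.5% in each direction. Assumed, because the documents give no rates: t, the proportion with a drug-related AE, and f, the proportion of uncured subjects with a disease complication.

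*1. Equal drug toxicity, any graded event.* With independence, P(event) = 1 − (1 − t)(1 − f·u). For t = 0.20 and f = 0.50:

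- test: 1 − 0.80 × 0.915 = 0.268
- control: 1 − 0.80 × 0.815 = 0.348
- chance of a significant result favouring test (pooled normal approximation): Φ[(0.080 − 0.159)/0.0807] = 16.5%

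| t | f = 25% | f = 50% | f = 75% | f = 100% |
|---|---|---|---|---|
| 10% | 10.3% | 23.3% | 40.0% | 58.1% |
| 20% | 7.5% | 16.5% | 29.4% | 45.6% |
| 30% | 6.2% | 12.6% | 22.4% | 35.7% |

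*2. Equal drug toxicity, ordinal test.* This is closer to the SAP's model. I assumed three levels for the worst grade per subject (none, I–II, III), drug events at I–II and disease complications at III, with f = 0.50. Grade III is then 0.5 × 17% = 8.5% on test and 0.5 × 37% = 18.5% on control. I simulated the rank score test that matches a proportional-odds model without age and sex. For t from 10% to 30%, the expected odds ratio is 0.56 to 0.67 in favour of test. A significant finding of less toxicity occurs in about 20% to 27% of runs.

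*3. Drug toxicity truly worse on test, 30% v 20%.* The drug-toxicity odds ratio is (0.30/0.70)/(0.20/0.80) = 1.71 against test.

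- Independent overlap: Grade I–II is 0.30 × 0.915 = 27.5% v 0.20 × 0.815 = 16.3%. Any event is 36.0% v 34.8%. The expected ordinal odds ratio is 0.90.
- No overlap: any event is 38.5% in both arms.

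A significant finding of less toxicity occurs in only about 5% to 7% of runs. What this case mainly shows is that the real excess disappears.

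*4. Drug toxicity truly better on test, 15% v 40%, with the same complication rate g in both arms.* Rates are 1 − 0.85(1 − g) and 1 − 0.60(1 − g).

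| g | Test | Control | Power |
|---|---|---|---|
| 0% | 15% | 40% | 90% |
| 20% | 32% | 52% | 64% |
| 40% | 49% | 64% | 41% |
| 60% | 66% | 76% | 24% |

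**The case against.** **The meaning of AETOXGR is not established.** This stands. Causality is also a five-point scale, so ordinal use alone does not settle it, and the annotated eCRF and Data Display Plan are not available here. A reader might infer that the SAP demonstrably counts severe keratitis complications as toxicity. The documents support only that the variable is undefined and most likely the intensity grade. On either reading, the tested endpoint needs a definition.

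**The documents do not grade the complications.** This also stands. A reader might infer that complications would take the highest grades and drug irritation the lowest. Protocol 8.1.5 says they are expected but assigns no grade. Protocol 8.2.1 grades by symptoms, intervention and daily activity, so scarring seen only on examination could be Grade I. The Phase 1 events that led to withdrawal were mild to moderate, which can reach Grade II. Signs present at consent are not AEs unless they recur after recovery or worsen significantly.

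**The causality tables already separate the two.** In part. SAP 7.10.2 plans counts of subjects with related AEs and a breakdown by causality, and SAP 7.10.7 to 7.10.12 report worsening, relapse, surgery and complications separately. A reader can therefore see drug-related events descriptively, but none of this enters the test.

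**Safety results are descriptive only.** That statement sits with the laboratory analyses (protocol 7.5.2; SAP 6.3.2 and 7.10.3). The AE hypothesis has its own null and decision rule.

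**Conclusion.** The concern holds with limits. The toxicity endpoint is undefined. On the most likely reading, the test mixes disease complications with drug effects, so it can mistake better efficacy for lower toxicity or mask a real excess.

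The size is conditional. With equal drug toxicity, the chance of a false finding of less toxicity is about 6% to 58% on any graded event and 20% to 27% in the ordinal setting, against a nominal 2.5%. These figures rest on assumed toxicity and complication rates, one worst grade per subject, the planned cure rates, and, in the ordinal case, complications at Grade III.

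A reader might infer that 0.08% PHMB will look less toxic whatever the truth, or that the test is simply a second measure of treatment failure. The 30% v 20% case does not support that: a significant result in favour of test is uncommon there, and the main effect is that the excess is hidden.

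This should be changed, as an amendment to a secondary safety test; the primary conclusion does not depend on it.

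**What to change.** In SAP 7.10.2, before unmasking:

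1. State what AETOXGR contains and which scale it uses.
2. Define a toxicity-related AE as one assessed as possible, probable or related under protocol 8.2.2. Show ocular events in the study eye separately, but do not drop non-ocular events.
3. State how the expected keratitis complications of protocol 8.1.5 are handled.
4. Test the proportion of subjects with at least one such AE.
5. Use AETOXGR only to describe severity within that set.

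The cost is SAP wording; causality is already collected for every AE. The drawback is reliance on the investigator's judgement under imperfect masking: the containers are not identical (protocol 5.6) and the allocation is opened at treatment failure (protocol 5.3.3). A prespecified list of toxicity terms, fixed before unmasking, could serve as a sensitivity analysis.
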